Protocol Synopsis

Study Title & ID	I ntravascular Ultrasound- G uided Intervention for Venous Leg U lcers (IGuideU) Protocol ID: 200202
Objectives	
The primary objective of this study is to determine whether the interrogation of the deep venous system (iliac-common femoral veins) for deep venous obstruction (DVO) by multiplanar venography (MPV) plus intravascular ultrasound (IVUS), with subsequent interventional treatment determined and guided by IVUS (interrogation group), results in improved clinical outcomes when compared to deferred interrogation of the deep venous system (deferred-interrogation group).
 
The secondary objectives are to assess changes in treatment decision parameters made with MPV after further investigation with IVUS and to assess the long-term clinical and economic impact of IVUS-guided interventional treatment for venous leg ulcers compared to the deferred-interrogation group.

Study Design	
Global, prospective, multi-center, randomized controlled trial. After signing a written informed consent, patients will be randomized 1:1 to either a deferred-interrogation group or to an interrogation group in which patients will be first evaluated with MPV imaging during iliac-common femoral vein assessment for possible endovascular intervention and then further interrogated with IVUS imaging. The treatment plan derived from venography alone will be compared to the treatment plan created with the addition of the IVUS information and any differences in treatment plan will be documented. Confirmation of whether or not the threshold of stenosis/occlusion required for endovenous stenting has been met will be determined by the IVUS imaging obtained. Any patients determined to require venous stenting will be stented according to the on-label manufacturer’s instructions for the use of IVUS in guiding stent sizing and placement.
 
This study will employ an independent core laboratory to evaluate, review and adjudicate all scheduled and unscheduled de-identified wound, MPV, and IVUS images. The study will also utilize a medical monitor to review and adjudicate peri-procedural serious adverse events (SAE).

Endpoints	
Primary Clinical Endpoint The primary clinical endpoint is the difference in complete ulcer healing between the interrogation group and the deferred-interrogation group at 3 months. Complete ulcer healing is defined as 100% epithelialization of the venous ulcer. Healing will not be assumed for any area of the wound where a scab is present.
 
Diagnostic Endpoint The diagnostic endpoint is a composite of the difference in DVO detection and the subsequent changes in treatment plan created based on the IVUS information in combination with MPV information versus the initial treatment plan created using the information from MPV alone. DVO is defined as $\geq 50\%$ diameter reduction in the deep venous system when assessed by MPV or $\geq 50\%$ reduction in cross-sectional area (CSA) of the deep venous system when assessed by IVUS.
 
Changes in the following parameters will be considered a changed in treatment plan:
 
 1. Location of the IVC confluence (common iliac vein/confluence interface) relative to vertebral bodies 2. Presence of significant disease ($\geq 50\%$ reduction in diameter and/or cross-sectional area) 3. Location of the disease

Document ID:	200202	Intravascular Ultrasound-Guided Intervention for Venous Leg Ulcers (IGuideU)		Classification:	For internal use
Modified:	13 Jan 2022	Clinical Investigation Protocol - ISO 14155		Author:	[name]
Version:	4.0	User Tool ID:	16.2.6UserTool0001	Page:	4 of 57
Status:	Final	User Tool Version Date:	08JUL2019		

Clinical Investigation Protocol

	
 4. Percentage (%) of obstruction/compression (compression or residual lumen diameter divided by reference vessel diameter) 5. Reference vessel and associated diameter/CSA 6. Length of disease (mm) 7. Decision to stent 8. Decision to pre- and/or post-dilate the occlusion 9. Number of stents to be used 10. Length(s) and Diameter(s) of stents to be used 11. Manufacturer and model of stent(s) to be used 12. Desired landing zones for stent placement 13. Diagnosis of PTS, NIVL, or other 
Secondary Endpoints The following are secondary endpoints:
 
 1. Rate of ulcer healing measured between groups at 3, 6, 12, 18 and 24 months. 2. Rate of ulcer healing for stented PTS and NIVL patients at 3, 6, 12, 18 and 24 months. 3. Recurring ulcers in both arms from 3 months out to follow-up visit 24 months provided each arm has at least 30 subjects. The choice of 30 is based on central limit theorem in order to have normally distributed data for descriptive summary statistics. 4. Recurring ulcers between PTS and NIVL sub-groups. 5. Change in QoL using EQ5D and SF-36 forms. 6. Change in clinical score will be assessed using the VCSS and CEAP scoring systems. 7. Medical resource utilization (MRU) and health economic analysis between the interrogation and deferred-interrogation arms. 
*Note: Every effort will be made to balance the enrollment of PTS and NIVL patients.


Subject Population
	
In order to have 212 evaluable subjects with a 20% projected attrition rate, up to 266 evaluable subjects will be enrolled and randomized.
 
Inclusion Criteria:
 
 1. Be ≥ 18 and ≤ 85 years of age. 2. Able and willing to participate and comply with the protocol, including the defined follow-up schedule, by signing an IRB or Ethics Committee approved informed consent form. 3. Active venous leg ulcer (CEAP C6). 4. Previously completed treatment for clinically significant reflux in the superficial and/or perforator venous system of the target limb ≥ 3 months prior to enrollment, if clinically indicated. 5. Completed at least 3 months of prescribed compression therapy after any ablation. 6. Palpable dorsalis pedis or posterior tibial artery (DP/PT) pulses at ipsilateral foot or ABI ≥ 0.8. 7. Be able to ambulate unassisted or with non-motorized assistive devices. 8. Current VLU present ≤ 48 months. 
Exclusion Criteria:
 
 1. Patient is known pregnant or breast-feeding or planning to become pregnant in the following year. 2. If antiplatelet and anticoagulation therapy cannot be tolerated. 3. Previous venous stent implantation involving the target limb, target lesion, or inferior vena cava. 4. Previous venovenous bypass surgery involving the target limb. 5. Previous endovascular recanalization of the target lesion segment 6. Known metal allergy precluding stent implantation.

Document ID:	200202	Intravascular Ultrasound-Guided Intervention for Venous Leg Ulcers (IGuideU)		Classification:	For internal use
Modified:	13 Jan 2022	Clinical Investigation Protocol - ISO 14155		Author:	[name]
Version:	4.0	User Tool ID:	16.2.6UserTool0001		
Status:	Final	User Tool Version Date:	08JUL2019	Page:	5 of 57

Clinical Investigation Protocol

	
 7. Known or suspected to have inadequate inflow to support stent patency in the target limb. 8. Active cancer diagnosis. 9. Known positive test for COVID-19 (Sars-CoV-2) within the last 2 weeks and actively symptomatic. 10. Known or suspected venous outflow obstruction caused by tumor compression/encasement with or without thrombus. 11. Known allergy to contrast media that cannot adequately be pre-medicated prior to study procedure. 12. Known Renal dysfunction (defined as eGFR <30 mL/min/1.73m²) that would preclude adequate contrast usage. 13. Diagnosed with right heart failure/pulmonary hypertension. 14. Has known clinically significant abnormal platelet count outside laboratory reference ranges. 15. Has known clinically significant abnormal WBC, fever, sepsis or positive blood culture. 16. Organ transplant requiring immunosuppressant therapy. 17. Unstable angina pectoris, or myocardial infarction within 30 days and/or hemorrhagic stroke within 3 months. 18. Subjects with an active diagnosis of osteomyelitis of the ipsilateral limb. 19. Previous or planned surgical or catheter-based procedure on index leg within 30 days before or 30 days after the index procedure. 20. Active participation in another investigational drug or device study. 21. Subject has any condition, which, in the opinion of the investigator, precludes the subject from participation.

Test Groups
	
 • Deferred-Interrogation Group: See guidelines below. • Interrogation Group: Compression therapy plus endovascular imaging (MPV+IVUS) with or without intervention (stenting). 
The deferred-interrogation group will continue to receive non-invasive therapies consisting primarily of compression therapy/stockings that would have otherwise been continued outside of this research protocol. Listed below are the protocol guidelines for deferred-interrogation therapies:
 
Mandate
 
 • Continued compression therapy/dressing as prescribed. 
Allow
 
 • Periodic leg elevation. • Sclerotherapy under ulcer bed. • Recommend mechanical debridement as needed. • Wound biopsy if evidence of infection. • Systemic antibiotics if patient is diagnosed with an infection, avoid prophylactic prescription. • Pain management medication (Pentoxifylline/Trental) allowed but not recommended • Topical antimicrobial as needed. 
Prohibit
 
 • Negative pressure systems. • Artificial and/or autologous skin grafting within first 3 months after randomization and within the first 3 months for subjects that crossover from the deferred-interrogation group to the interrogation group. • Skin substitutes and tissue-based therapies within first 3 months after randomization and within the first 3 months for subjects that crossover from the deferred-interrogation group to the interrogation group. • Experimental topical creams and lotions.

Document ID:	200202	Intravascular Ultrasound-Guided Intervention for Venous Leg Ulcers (IGuideU)		Classification:	For internal use
Modified:	13 Jan 2022	Clinical Investigation Protocol - ISO 14155		Author:	[name]
Version:	4.0	User Tool ID:	16.2.6UserTool0001	Page:	6 of 57
Status:	Final	User Tool Version Date:	08JUL2019		

Clinical Investigation Protocol

	
 Growth factors within first 3 months after randomization and within the first 3 months for subjects that crossover from the deferred-interrogation group to the interrogation group. 											
Schedule of Assessments	There are 6 in-person visits planned for this clinical study, including the screening visit. The study is anticipated to last a total of 24 months for each enrolled study											
		Screening Visit	Baseline Visit/Index Procedure	1 Month (30 days)	3 Months (90 days)	6 Months (180 days)	12 Months (365 days)	18 Months (545 days)	24 Months (720 days)	Early Termination Visit*	Unscheduled Visit*	Re-intervention Procedure*
	Visit Window	-30 to 0 days	0 days	±14 days	±14 days	±30 days	±30 days	±30 days	±30 days	NA	NA	NA
	Visit Type	Office	Hospital/OBL	Office	Office	Office	Office	Phone Call	Phone Call	Office/Hospital/OBL	Office/Hospital/OBL	Hospital/OBL
	Informed Consent	X										
	Medical History	X										
	Eligibility/Inclusion and Exclusion Criteria	X										
	Urine Pregnancy Test ^a		X									
	Enrollment and Randomization	X										
	Duplex Ultrasound ^b			X	X	X	X					
	Physical examination	X		X	X	X	X			X	X	
	Anticoagulant and Antiplatelet	X	X	X	X	X	X	X	X	X ^h	X ^h	X ^h
	Clinical Laboratory Tests ^c		X									
	Venous Ulcer Assessment	X	X	X	X	X	X			X ^h	X ^h	X ^h
	Venous Ulcer Imaging		X	X	X	X	X			X ^h	X ^h	X ^h
	CEAP Clinical Category	X	X	X	X	X	X			X ^h	X ^h	X ^h
	VCSS Category	X	X	X	X	X	X			X ^h	X ^h	X ^h
	Study Visit Questionnaire			X	X	X	X			X ^h	X ^h	X ^h
	Wound Care Management Education ^d		X	X	X	X	X					
	SF-36		X							X ^h	X ^h	X ^h
EQ5D Questionnaire		X							X ^h	X ^h	X ^h	
Phone Call Questionnaire							X	X				
MPV Imaging ^e		X										

Document ID:	200202	Intravascular Ultrasound-Guided Intervention for Venous Leg Ulcers (IGuideU)		Classification:	For internal use
Modified:	13 Jan 2022	Clinical Investigation Protocol - ISO 14155		Author:	[name]
Version:	4.0	User Tool ID:	16.2.6UserTool0001	Page:	7 of 57
Status:	Final	User Tool Version Date:	08JUL2019		

[figure not shown]
Clinical Investigation Protocol

	IVUS Imaging ^e		X										
	Adverse Events ^f		X										
	Patient-completed Diary ^g SF-36 Questionnaire ^h EQ5D Questionnaire ⁱ	Completed monthly for study duration, through 24 months											

Abbreviations: CEAP - Clinical Etiology Anatomy Pathology, EQ5D – EuroQol 5 Dimensions; IVUS – intravascular ultrasound, MPV – multi- planar venography, SF-36 – Short form 36; VCSS – Venous Clinical Severity Score.
 
*Note: While an attempt should be made to collect all non-invasive testing at unscheduled visits, early termination visits, or re-interventions, a protocol deviation will not be required if all assessments are not completed.
 
^aUrine pregnancy test shall be taken on all females of childbearing prior to the index procedure.
 
^bIn all follow-up visits, DUS will be performed on the patients who received a stent implantation as part of the index procedure to assess stent patency and position.
 
^cClinical laboratory tests include: Serum creatinine and eGFR. These laboratory tests must be performed within 30 days of the index procedure.
 
^dStudy personnel will provide guidance on wound care management best practices according to the site/facility guidelines.
 
^eMPV and IVUS imaging will only be performed on patients receiving an index-procedure per the study protocol.
 
^fAdverse Event reporting is for peri-procedural events and IVUS-related adverse events (<48 after index-procedure).
 
^gSubjects will be provided with a diary at the baseline visit. The diary is designed to be completed on a monthly basis, as well as following any contact with the health care system related to treatment of his/her venous leg ulcer. The diary will be used to track major events, such as compliance to compression therapy and other notes related to the index ulcer. The diary also requires completion of the quality-of-life questionnaires (EQ-5D, SF-36). The diary will be reviewed at each office visit after the initial receipt. After the last in-person study visit, any hard-copy diaries will be sent to the study site coordinator on a monthly basis until the 24-month study completion.
 
^hFor early termination, unscheduled follow-up visits, and/or re-intervention procedures every attempt should be made to obtain the following assessments: Antiplatelet and Anticoagulant use; Study Visit Questionnaire; Venous Ulcer Assessment including venous ulcer imaging; CEAP clinical category, VCSS category, and the SF-36 and EQ5D Questionnaires.
 
ⁱ Questionnaires should be completed in the diary. If not completed in the diary, the subject should complete the questionnaires at the time of the visit.
 
^j Screening and baseline visits can be combined
													

At-Home Subject Procedures
	
 • Diary of compliance with standard of care procedures, wound care management, quality of life questionnaires, and medical resource use questions. • Follow-up phone call at 18 and 24 months. 												

Document ID:	200202	Intravascular Ultrasound-Guided Intervention for Venous Leg Ulcers (IGuideU)		Classification:	For internal use
Modified:	13 Jan 2022	Clinical Investigation Protocol - ISO 14155		Author:	[name]
Version:	4.0	User Tool ID:	16.2.6UserTool0001	Page:	8 of 57
Status:	Final	User Tool Version Date:	08JUL2019		

Study Schematic

The following diagram illustrates the sequence of evaluations and follow-up visits for study participants:

Document ID:	200202	Intravascular Ultrasound-Guided Intervention for Venous Leg Ulcers (IGuideU)		Classification:	For internal use
Modified:	13 Jan 2022	Clinical Investigation Protocol - ISO 14155		Author:	[name]
Version:	4.0	User Tool ID:	16.2.6UserTool0001	Page:	9 of 57
Status:	Final	User Tool Version Date:	08JUL2019

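### Does the absence of a named covariate for 3-month ulcer healing leave the primary comparison less precise than it should be?

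*Combined protocol and SAP*

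**What the plan says.** All references are to the Protocol Synopsis.

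- **Endpoints row, first entry:** the main outcome is set out as follows: "The primary clinical endpoint is the difference in complete ulcer healing between the interrogation group and the deferred-interrogation group at 3 months". Healing is binary (full epithelialisation). No test or model is attached to it.
- **Study Design:** "patients will be randomized 1:1 to either a deferred-interrogation group or to an interrogation group". No stratification factor is named.
- **Subject Population:** "In order to have 212 evaluable subjects with a 20% projected attrition rate", up to 266 are to be randomised. The healing rates, alpha and power behind 212 are not given.
- **Inclusion Criterion 8:** "Current VLU present ≤ 48 months". Neither criteria list sets a minimum or maximum ulcer area.
- **Secondary Endpoints, note:** "Every effort will be made to balance the enrollment of PTS and NIVL patients". This is the only statement on balance, and it concerns aetiology at enrolment.
- **Schedule of Assessments:** "Enrollment and Randomization", "Venous Ulcer Assessment" and "VCSS Category" are all marked at Screening. Ulcer imaging is first marked at the baseline visit. Screening may fall up to 30 days before baseline, although footnote j lets the two visits be combined.

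**The concern.** Eligible ulcers can differ widely in age, and in size as far as the criteria lists show. If age and size predict healing at 3 months, an unadjusted difference leaves explainable variation in the error term. The confidence interval is then wider, and power lower, than the same patients could give. Adjusting for baseline covariates costs no extra patients and almost no variance when the covariates turn out to be uninformative. It must, however, be fixed in advance. A synopsis that admits such a mixed population and names no covariate therefore looks like a missed opportunity in a trial with about 106 evaluable patients per arm.

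**Working it through.** **1. The plan's own figure.** 212 / (1 - 0.20) = 265. Rounding up per arm: 106 / 0.80 = 132.5, so 133, and 2 × 133 = 266, which matches. The 212 itself cannot be rebuilt uniquely. For example, 35% vs 55% and 45% vs 65% (two-sided 5%, 80% power, continuity-corrected) and 40% vs 60% (one-sided 5%, 90% power) all give 212. The design assumptions evidently lie outside the synopsis, and the analysis method may lie there too.

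**2. What adjustment could gain, by formula.** Assume two-sided 5%, 80% unadjusted power, and covariates explaining a share R² of the outcome variance. The adjusted variance is then about (1 - R²) times the unadjusted one, and power = Φ[(1.960 + 0.842)/√(1 - R²) - 1.960].

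| Assumed R² | SE ratio | Power | Equivalent evaluable N = 212/(1 - R²) |
|---|---|---|---|
| 0 | 1.000 | 80.0% | 212 |
| 0.02 | 0.990 | 80.8% | 216 |
| 0.05 | 0.975 | 82.0% | 223 |
| 0.10 | 0.949 | 84.0% | 236 |
| 0.20 | 0.894 | 87.9% | 265 |

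For R² = 0.10: 2.802/0.949 - 1.960 = 0.993, and Φ(0.993) = 84.0%.

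**3. The same by simulation.** The estimator was a logistic model standardised to a marginal risk difference, with N = 212 and 4,000 trials per scenario. The covariates were independent and measured without error. Assumed rates were 40% vs 59.3% and 30% vs 48.6%. The table gives the variance ratio, adjusted over unadjusted, for the two pairs of rates in that order.

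| Assumed odds ratio per SD, each covariate | Duration only | Duration and area |
|---|---|---|
| 1 (no prognostic value) | 1.005, 1.003 | 1.011, 1.010 |
| 0.80 | 0.993, 0.997 | 0.990, 0.986 |
| 0.67 | 0.972, 0.975 | 0.926, 0.935 |
| 0.50 | 0.936, 0.939 | 0.832, 0.855 |

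Duration alone thus runs from no gain to about 6%. Reaching about 17% with duration alone took a log-odds slope of 1.0 per SD, an odds ratio of exp(-1.0) = 0.37.

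Allowing for imperfect area data (80% reliable, 10% missing; 40% vs 59.1%), slopes of 0.3 for each covariate cut the variance by 2.8% and narrowed the mean 95% interval from 26.6 to 26.1 points. Slopes of 0.6 cut it by 11.3%, to 25.0 points.

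**4. Is a usable covariate shown to exist before allocation?**

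- *Duration:* Criterion 8 can be applied with a yes or no against 48 months. The synopsis does not say that months are recorded.
- *Area:* the content of the screening ulcer assessment is not given, and imaging starts at baseline, which can come after randomisation.
- *VCSS:* this is marked at Screening, the visit that also carries randomisation, but the synopsis does not say how well it predicts healing. The calculations above do not cover it.

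**5. Does the text show an unadjusted analysis?** The endpoint sentence names a contrast. A difference in healing proportions is compatible with an unadjusted test, a stratified test or a standardised adjusted estimate. The synopsis does not choose among them.

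**The case for a change.** The strongest case for the concern is the asymmetry. Uninformative covariates cost about 1% in variance. Moderately prognostic ones (slope 0.6 per SD) save about 6% with duration alone and about 11% with area as well. The trial already randomises up to 266 to secure 212, so extra precision from the same patients has value. Adjustment keeps type I error sound (4.7% to 5.5% in simulation), and standardisation preserves the marginal difference that the endpoint names. Covariates chosen after the outcomes are seen would lack credibility, so the time to ask is before the analysis.

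This arithmetic stands, and so does the general advice. It does not establish a fault in this plan. A recommendation that applies only if an unseen section does not already adjust, and then only to whichever covariate turns out to be recorded in time, is a question rather than an identified weakness. The documents show that duration, and perhaps size, can vary between patients. They do not say that either predicts healing, and the assumed range includes no gain at all.

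**Conclusion.** The concern does not hold. The missing covariate reflects how much text is available: the synopsis is equally silent on the test, alpha, power and healing rates. An unadjusted difference would in any case be valid under 1:1 randomisation, so no bias, contradiction or invalid inference arises.

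The possible gain runs from a cost of about 1% in variance to a saving of about 17%. With weak covariates the saving is about 1% to 3%, roughly half a point off a 26.6-point interval. These figures rest on assumed healing rates of 30% to 40% in the deferred-interrogation group, two-sided 5%, about 80% power and assumed prognostic strength, none of which the documents state. The larger savings need either very strong prognosis from duration or an area measurement that is not shown to precede allocation. The sponsor may be asked whether the full statistical section pre-specifies baseline covariates, but the text gives no ground for recording a deficiency.

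### The schedule does not require SF-36 and EQ5D before randomisation, so the baseline for change in QoL can follow allocation

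*Combined protocol and SAP*

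**What the plan says.** All references are to the Protocol Synopsis.

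- Endpoints, secondary endpoint 5: "Change in QoL using EQ5D and SF-36 forms". It names no baseline, time point or method of analysis.
- Schedule of Assessments: the row "Enrollment and Randomization" is marked in the screening column only, with a window of -30 to 0 days.
- Schedule of Assessments: the rows SF-36 and "EQ5D Questionnaire" have no screening mark. Each is first marked under "Baseline Visit/Index Procedure", at 0 days.
- Footnote g: the diary that holds both questionnaires is first given to the patient at the baseline visit and is then filled in monthly. Footnote i: forms missed in the diary are completed at the visit. Neither footnote refers to randomisation or to the procedure.
- Footnote j: "Screening and baseline visits can be combined". It gives no order of steps within the combined visit.
- "Venous Ulcer Assessment", CEAP and VCSS are marked at both screening and baseline.
- Study Design and Test Groups: allocation is 1:1 after consent. One arm has catheter-based imaging with or without stenting, and the other continues compression. The synopsis describes no sham procedure and no masking of patients.

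**The concern.** A change score is protected by randomisation only if its starting value cannot depend on the arm. SF-36 and EQ5D are self-reported. A patient who knows the allocation may score differently because a procedure is imminent or because investigation has been deferred. The setting can differ as well: interrogation patients have the forms scheduled for the day of an invasive procedure, and deferred patients for a day without one. The forms are not required to precede the procedure.

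QoL is collected monthly to 24 months, so one shifted baseline would enter every later change from baseline. Where the visits are separate, a patient who is randomised but leaves before day 0 has no baseline QoL at all. This bears on a secondary endpoint, not on the primary one.

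**Working it through.** **1. Order of events in the schedule**

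| Item | Screening (-30 to 0 days) | Baseline/index procedure (0 days) |
|---|---|---|
| Randomisation | marked | – |
| SF-36, EQ5D | – | first mark |
| QoL diary handed out | – | yes (footnote g) |
| Ulcer assessment, CEAP, VCSS | marked | marked |
| Wound photograph | – | first mark |

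Separate visits: QoL follows randomisation by up to 0 - (-30) = 30 days. Combined visit: either order is possible. In neither case does the text require QoL before allocation is revealed or before the procedure.

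**2. The plan's own figure**

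The synopsis inflates 212 evaluable patients for 20% attrition: 212 / (1 - 0.20) = 265, or 266 when rounded up to an even number for 1:1 allocation. This agrees with the stated 266. It gives 212 / 2 = 106 evaluable and 266 / 2 = 133 randomised per arm. The point about visit order does not depend on these figures. They only scale the illustration.

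**3. How a baseline shift would carry through**

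Assumptions, not from the documents: no true effect; equal SDs, so results are in SD units; n = 106 per arm; two-sided 5% test; a shift of s SD at baseline in one arm only, gone by follow-up; baseline to follow-up correlation r of 0.3 to 0.7.

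- Change score: bias = s; SE = √(2(1 - r)) × √(2/n).
- ANCOVA: bias = r × s; SE = √(1 - r²) × √(2/n).
- False-positive rate = 1 - Φ(1.960 - bias/SE) + Φ(-1.960 - bias/SE).

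Example with s = 0.2 and r = 0.5, where √(2/106) = 0.137:

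- Change score: SE = 1.000 × 0.137 = 0.137; bias/SE = 1.46; rate 30.7%.
- ANCOVA: bias = 0.5 × 0.2 = 0.10; SE = 0.866 × 0.137 = 0.119; bias/SE = 0.84; rate 13.4%.

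| r | s | Change score: bias | Change score: rate | ANCOVA: bias | ANCOVA: rate |
|---|---|---|---|---|---|
| 0.3 | 0.1 | 0.10 | 9.4% | 0.03 | 5.6% |
| 0.3 | 0.2 | 0.20 | 23.4% | 0.06 | 7.4% |
| 0.3 | 0.3 | 0.30 | 45.5% | 0.09 | 10.6% |
| 0.5 | 0.1 | 0.10 | 11.3% | 0.05 | 7.0% |
| 0.5 | 0.2 | 0.20 | 30.7% | 0.10 | 13.4% |
| 0.5 | 0.3 | 0.30 | 58.9% | 0.15 | 24.3% |
| 0.7 | 0.1 | 0.10 | 15.6% | 0.07 | 11.0% |
| 0.7 | 0.2 | 0.20 | 46.8% | 0.14 | 29.7% |
| 0.7 | 0.3 | 0.30 | 80.5% | 0.21 | 57.2% |

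**4. Would a shift be visible?**

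With 133 per arm, the SE of the baseline difference is √(2/133) = 0.123 SD. Shifts of 0.1, 0.2 and 0.3 SD are then about 0.8, 1.6 and 2.4 SE. A large one-arm shift would probably show as a baseline imbalance. A small one could pass as chance.

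**The case against.** The strongest reply has four parts.

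- **Visits may be combined.** A site could then collect the forms first. This stands: it would be wrong to infer that the QoL baseline always follows randomisation. But combining is optional and no order is set, so a baseline before allocation is possible and not secured.
- **Masking and order may be settled elsewhere.** The text reviewed is the synopsis, pages 4 to 9 of 57. That patients know their arm is inferred from the design. The documents do not state it, nor when patients are told. This stands as a limit on certainty.
- **The analysis may avoid the problem.** Endpoint 5 names no between-arm change score. ANCOVA would remove 30% to 70% of the bias at correlations of 0.7 to 0.3, and a direct comparison of follow-up scores between arms needs no baseline. This stands, but the endpoint is worded as a change, and ANCOVA leaves a remainder.
- **A shift would show.** Partly so, as step 4 indicates. A reader might infer that any shift is undetectable, and that is too strong.

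Three further readings are tempting but unsupported. The first is that the late photograph compromises healing: it does not enter QoL change, and the primary endpoint is complete healing at 3 months, not change from a baseline image. The second is that EQ5D feeds the economic analysis: secondary endpoint 7 names no EQ5D input. The third is that the other screening measures are already safe. CEAP C6 must precede randomisation because it is an inclusion criterion, but VCSS shares the randomisation column with no stated order.

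**Conclusion.** The point holds in a limited form. The schedule does not secure an SF-36 or EQ5D score before randomisation. With separate visits, the only QoL baseline for secondary endpoint 5 follows allocation by up to 30 days and, in the interrogation arm, falls at the procedure visit. With a combined visit, the order is open.

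The size is conditional. The bias equals the one-arm shift for a change score, and correlation times shift for ANCOVA. Across assumed shifts of 0.1 to 0.3 SD and correlations of 0.3 to 0.7, the false-positive rate runs from about 9% to 80% for change scores and 6% to 57% for ANCOVA. The documents give no evidence that a shift occurs, and no SD or correlation from which to narrow the range. The conclusion also assumes that patients know their arm and that the full protocol does not already fix the order. It is a cheap improvement to a secondary endpoint, not a flaw in the primary comparison.

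**What to change.** In the Schedule of Assessments, mark the first SF-36 and EQ5D under screening. Add a footnote that both are completed after consent and before allocation is revealed, including when screening and baseline are combined. Define these scores as the baseline for secondary endpoint 5.

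If the screening VCSS and CEAP are to serve as baseline for secondary endpoint 6, require them before randomisation in the same footnote. A wound photograph before randomisation is an optional addition to the core laboratory record and is not needed for QoL change or for 3-month healing.

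The cost is one amendment to the schedule. The forms and the office visit already exist. The downside is that patients who fail screening will also complete the forms. The change must come before enrolment to help every patient, because a baseline from before allocation cannot be recovered afterwards.

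### Three wound-therapy restrictions are counted from randomisation, but the primary 3-month read-out is counted from baseline/index, so as written the restrictions can end before healing is judged, by at most 44 days

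*Combined protocol and SAP*

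**What the plan says.** **Restrictions (Protocol Synopsis, Test Groups, Prohibit list).** Three items carry a time limit counted from randomisation:

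- "Artificial and/or autologous skin grafting within first 3 months after randomization"
- "Skin substitutes and tissue-based therapies within first 3 months after randomization"
- "Growth factors within first 3 months after randomization"

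Each adds a further 3-month period for patients who cross over from deferred interrogation to interrogation. Two other items, negative pressure systems and experimental topical products, have no time limit and are not affected. The list is introduced as guidance for the deferred-interrogation therapies.

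**Visit clock (Schedule of Assessments).** "Enrollment and Randomization" is marked in the Screening Visit column only, with a window of -30 to 0 days. The column "Baseline Visit/Index Procedure" stands at 0 days. The 3-month visit is at 90 days, ±14. Footnote j allows screening and baseline to be combined but does not require it.

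**Primary endpoint (Endpoints).** It is the "difference in complete ulcer healing between the interrogation group and the deferred-interrogation group at 3 months". Healing means full epithelialisation, and a scabbed area does not count as healed. The sentence does not say from which day the 3 months are counted.

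**The concern.** The time-limited restrictions last 3 months and the primary endpoint is read at 3 months, so a reader would expect the first to cover the second. The two periods start on different days. Randomisation may precede Day 0 by up to 30 days, and the visit itself may fall up to 14 days after its nominal day. Both push the read-out past the end of the restrictions.

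The three restricted items are wound therapies, and the endpoint is wound closure. If the list is followed to the letter, a patient could start one of them after the restriction has ended and before the primary assessment, with no protocol deviation. Healing at that assessment would then no longer be observed wholly under the restricted conditions, and the synopsis does not say whether this is intended. This is a consequence of a rule that is stated, not of detail left out.

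**Working it through.** The plan states no figure for the interval between the end of the restrictions and the read-out, so there is none to reproduce. The interval follows by addition.

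**Inputs**

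- Restriction period: 3 months from randomisation (Test Groups), taken as 90 days because the schedule equates 3 months with 90 days.
- Gap *g* from randomisation to Day 0: 0 to 30 days (screening window; footnote j makes 0 possible).
- 3-month visit: day 90 + *v*, with *v* from -14 to +14 (Schedule of Assessments).
- Follow-up days are counted from the baseline/index visit. This is read from the 0-day column; no sentence in the supplied text states it.

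**Formulas**

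- Read-out, in days after randomisation = *g* + 90 + *v*
- Uncovered days = max(0, (*g* + 90 + *v*) - 90) = max(0, *g* + *v*)

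**Results**

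| Gap *g* (days) | Read-out, days after randomisation | Uncovered days before read-out |
|---|---|---|
| 0 | 76 to 104 | 0 to 14 |
| 7 | 83 to 111 | 0 to 21 |
| 14 | 90 to 118 | 0 to 28 |
| 30 | 106 to 134 | 16 to 44 |

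The earliest read-out is 0 + 90 - 14 = 76 days after randomisation and the latest is 30 + 90 + 14 = 134. The maximum uncovered time is 134 - 90 = 44 days.

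**Sensitivity to the length of 3 months.** If 3 calendar months are 89 to 92 days, the maximum moves from 134 - 89 = 45 down to 134 - 92 = 42 days. With no gap, the maximum is 104 - 89 = 15 down to 104 - 92 = 12 days.

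**Does the gap alone explain the mismatch?** No. With *g* = 0 the visit window still leaves up to 14 days, so a common starting day would not by itself make the two periods agree.

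**Does the crossover clause close it?** Not for patients who have not crossed over. Their only stated limit is the one counted from randomisation.

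**The case against.** The strongest reply has four parts.

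1. *The long gap is least likely where the list most clearly applies.* The list is introduced for the deferred-interrogation therapies. Footnote e limits venography and IVUS to patients having an index procedure, so a deferred patient has no procedure slot to wait for, and footnote j allows a same-day baseline. This stands as a reason not to treat 44 days as typical. It does not remove the mismatch: the schedule gives that arm no shorter screening window, and up to 14 days remain with no gap at all.

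2. *A residue of up to 14 days arises for any fixed period read at a visit with a window.* True. It still lets a restricted therapy start before the primary assessment, and one sentence can deal with it.

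3. *Nothing shows that it matters to the result.* Starting a therapy is permitted, not required, and it would have to change complete closure before the visit. This stands. The documents give no rate of use, so no effect on the healing difference can be stated.

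4. *Only pages 4 to 9 of 57 were supplied, and the study schematic is not shown.* The protocol body may settle the point. This stands, and the finding is limited to the synopsis.

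Three stronger readings are tempting, but the text does not support them.

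- *The comparison is biased towards one arm.* Both arms share the same window, and no gap is reported for either. The plan permits a longer gap where a procedure must be scheduled but does not show one.
- *The primary endpoint has no time origin.* The endpoint sentence gives none, but the schedule's 0-day column largely supplies it.
- *Ulcers that heal before Day 0 distort the result.* Ulcer assessment is repeated at baseline, so such healing would be seen. An ulcer still closed at 3 months meets the healing definition on its face. Any size put on this would rest on assumed gaps and healing rates.

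**Conclusion.** The point holds as a conflict between two parts of the synopsis and should be fixed. As written, the three restrictions can end before the primary assessment: by 0 to 14 days with no gap between randomisation and Day 0, and by 16 to 44 days with the full 30-day gap. The 44-day figure needs the longest gap and the last permitted visit day together.

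This rests on two readings: 3 months is 90 days, and follow-up days count from the baseline/index visit. The first moves the maximum by no more than 2 days either way. The effect on the healing comparison is unknown and cannot be derived from the documents. Whether the mismatch affects one arm or both depends on the scope of the list, which the supplied text leaves open for patients randomised to interrogation. Confidence is medium, because the protocol body was not available.

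**What to change.** **Main change.** Reconcile Test Groups with the Schedule of Assessments so that the restriction period is expressly related to the primary 3-month assessment, including its ±14-day window. State whether the list binds both arms or only the deferred-interrogation arm. Which therapies are restricted, for how long and from which day are for the sponsor to decide. If the protocol body already settles these points, align the synopsis to it.

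**Minor clarifications.** State in the endpoint sentence whether 3 months counts from Day 0 or from another day. Apply one counting rule, the same in both arms, to ulcers healed before Day 0.

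**Cost.** A short text edit in Test Groups and a sentence or two in Endpoints. These edits by themselves change neither the sample size nor the visit schedule.
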